10.5.3 Interim Analyses and Pausing Guidelines

There will be no planned interim analyses for testing the primary hypotheses. Participants will be monitored for adherence to pre-ET and for pre/post response data capture. Pre-operative ET treatment adherence is expected to be close to 100% thus an indication of a lower rate would be cause for pause. After accrual of 50% of eligible participants, if the upper limit of a 90% CI around the adherence rate does not contain 80% then the study will be paused to assess the cause, which may result in no modification, study modification or closure. Similarly, the study will be monitored for any indication that use of 3 months of pre-ET negatively impacts surgical completion with the same decision guideline.

11 REGULATORY AND OPERATIONAL CONSIDERATIONS

11.1 Regulatory and Ethical Considerations

11.1.1 Informed Consent Document

Consent forms will be written in accordance with federal regulations and will be reviewed and approved by the IRB-HSR prior to use. Participants will be given a consent form to review and a

Pre-Operative Window of Adjuvant Endocrine Therapy to Inform Radiation Therapy Decisions in Older Women with Early-Stage Breast Cancer

Version Date: 21 February 2023

member of the study team will be available to answer any questions. Informed consent will be obtained from each participant prior to conducting any study-specific procedures or administering study treatment.

Signed consent forms and other research records will be retained in a confidential manner.

11.1.2 Consent Procedures and Documentation

Informed consent is a process that is initiated prior to the individual's agreeing to participate in the study and continues throughout the individual's study participation. Consent forms will be Institutional Review Board (IRB)-approved and the participant will be asked to read and review the document. A member of the study team will explain the research study to the participant and answer any questions that may arise. A verbal explanation will be provided in terms suited to the participant's comprehension of the purposes, procedures, and potential risks of the study and of their rights as research participants. Participants will have the opportunity to carefully review the written consent form and ask questions prior to signing. The participants should have the opportunity to discuss the study with their family or surrogates or think about it prior to agreeing to participate. The participant will sign the informed consent document prior to any procedures being done specifically for the study. Informed consent may be done via Telemedicine. Results from procedures completed prior to consent for standard of care purposes may be used for research purposes. Participants must be informed that participation is voluntary and that they may withdraw from the study at any time, without prejudice. A copy of the informed consent document will be given to the participants for their records. The informed consent process will be conducted and documented in the source document (including the date), and the form signed, before the participant undergoes any study-specific procedures. The rights and welfare of the participants will be protected by emphasizing to them that the quality of their medical care will not be adversely affected if they decline to participate in this study.

11.1.3 Confidentiality and Privacy

Participant confidentiality and privacy is strictly held in trust by the participating investigators and their staff. This confidentiality is extended to cover testing of biological samples and genetic tests (if applicable) in addition to the clinical information relating to participants. Therefore, the study protocol, documentation, data, and all other information generated will be held in strict confidence. Consents will be maintained in a confidential manner in accordance with the code of federal regulations and HIPAA. When possible, specimens will be coded with IDs (not MRN or name). No information concerning the study or the data will be released to any unauthorized third party without prior written approval of the Principal Investigator.

All research activities will be conducted in as private a setting as possible.

The study monitor, other authorized representatives of the Principal Investigator, representatives of the Institutional Review Board (IRB), or regulatory agencies may inspect all documents and records required to be maintained by the investigator, including but not limited to, medical records (office, clinic, or hospital) and pharmacy records for the participants in this study. The clinical study site will permit access to such records.

The study participant's contact information will be securely stored at each clinical site for internal use during the study. At the end of the study, all records will continue to be kept in a secure

Pre-Operative Window of Adjuvant Endocrine Therapy to Inform Radiation Therapy Decisions in Older Women with Early-Stage Breast Cancer

Version Date: 21 February 2023

location for as long a period as dictated by the reviewing IRB, Institutional policies, or sponsor requirements.

Study participant research data, which is for purposes of statistical analysis and scientific reporting, will be transmitted to and stored in OnCore. This will not include the participant's contact or identifying information. Rather, individual participants and their research data will be identified by a unique study identification number. The study data entry and study management systems used by the University of Virginia Cancer Center, Office of Clinical Research research staff will be secured and password protected.

To further protect the privacy of study participants, a Certificate of Confidentiality will automatically be issued by the National Institutes of Health (NIH) and an application is not necessary. This certificate protects identifiable research information from forced disclosure. It allows the investigator and others who have access to research records to refuse to disclose identifying information on research participation in any civil, criminal, administrative, legislative, or other proceeding, whether at the federal, state, or local level. By protecting researchers and institutions from being compelled to disclose information that would identify research participants, Certificates of Confidentiality help achieve the research objectives and promote participation in studies by helping assure confidentiality and privacy to participants.

11.1.4 Future Use of Stored Specimens and Data

Data collected for this study will be analyzed and stored at the University of Virginia.

At the end of the study, all study data will be archived and maintained by the PI in accordance with institutional policies.

11.1.5 Safety Oversight and Monitoring

The University of Virginia Cancer Center Data and Safety Monitoring Committee (CC DSMC) will provide oversight of the conduct of this study. The CC DSMC will report to the UVA Protocol Review Committee (PRC).

The UVA CC DSMC will review the following:

- All adverse events
- Audit results
- Application of study designed stopping/decision rules
- Whether the study accrual pattern warrants continuation/action
- Protocol violations

The UVA CC DSMC will meet every month for aggregate review of data. Tracking reports of the meetings are available to the PI for review. Issues of immediate concern by the DSMC are brought to the attention of the Principal Investigator (and if appropriate to the PRC and IRB) and a formal response from the Principal Investigator is requested. Per the UVA Cancer Center NIH approved institutional plan, this study will be audited approximately every 6 months. The audit may include direct access to source data/documents.

Pre-Operative Window of Adjuvant Endocrine Therapy to Inform Radiation Therapy Decisions in Older Women with Early-Stage Breast Cancer

Version Date: 21 February 2023

Any study under the purview of the University of Virginia HSR-IRB is subject to review. Studies are chosen for Post-approval Monitoring either a) at random or b) requested by a study team member or any member of the IRB-HSR.

The purpose of Post-approval Monitoring audits is to ensure that documentation of clinical research studies is of the highest quality, verify protocol adherence, and ensure that all Federal and local rules concerning clinical research are being fulfilled. Post-approval monitoring is done by staff within the office of the Vice President for Research (VPR) in accordance with their Standard Operating Procedures. The conduct of an on-site review may include but is not limited to:

- requests for progress reports from investigators,
- examinations of research records, including signed informed consent documents, protocol modifications, and unexpected, serious, and/or related adverse experience reports,
- contacts with research subjects, or
- observation of the consent process and/or research procedures. Examples of when observation of the consent process could occur are:
 - Full board IRB determines during review of a project that a conflict of interest exists such that the informed consent process should be observed by a neutral party;
 - IRB is made aware of a complaint or concern with regard to the informed consent process; or
 - IRB determines as a result of the monitoring process that the consent process is insufficient and education/training is required for conduct of consent.

Additionally, clinical site monitoring is conducted to ensure that the rights and well-being of trial participants are protected, that the reported trial data are accurate, complete, and verifiable, and that the conduct of the trial is in compliance with the currently approved protocol/amendment(s), with International Conference on Harmonisation Good Clinical Practice (ICH GCP), and with applicable regulatory requirement(s).

- The UVA Coordinating Center will implement ongoing monitoring activities for this study to ensure that Participating Institutions are complying with regulatory and protocol requirements, data quality, and subject safety. Monitoring will occur before the clinical phase of the protocol begins, continue during protocol performance and through study completion.
- Monitoring may be conducted either remotely or on-site. For remote visits, each institution will be required to provide redacted source documents for review or appropriate access to the EMR. The UVA MCRO will provide the Participating Institution with a follow-up letter following completion of the monitoring visit which should be maintained in the site regulatory files. The schedule for monitoring may be adjusted according to subject accrual and data quality. The Investigator will be notified in advance of each visit.
- Independent audits may be conducted by each institution according to institutional guidelines. Results of these audits may be requested by the UVA Coordinating Center.

11.1.6 Quality Assurance and Quality Control

Pre-Operative Window of Adjuvant Endocrine Therapy to Inform Radiation Therapy Decisions in Older Women with Early-Stage Breast Cancer

Version Date: 21 February 2023

The clinical site will perform internal quality management of study conduct and data, documentation and completion according to institutional policies.

Quality control (QC) procedures will be implemented beginning with the data entry system and data QC checks that will be run on the database will be generated. Any missing data or data anomalies will be communicated to the study team for clarification/resolution.

Following written Standard Operating Procedures (SOPs), the monitors will verify that the clinical trial is conducted and data are generated and biological specimens are collected, documented (recorded), and reported in compliance with the protocol, International Conference on Harmonisation Good Clinical Practice (ICH GCP), and applicable regulatory requirements (e.g., Good Laboratory Practices (GLP), Good Manufacturing Practices (GMP)).

The investigational site will provide direct access to all source data/documents, and reports for the purpose of monitoring and auditing, and inspection by local and regulatory authorities.

11.2 Data Handling and Record Keeping

11.2.1 Data Collection and Management Responsibilities

Data collection is the responsibility of the clinical trial staff at the site under the supervision of the site investigator. The investigator is responsible for ensuring the accuracy, completeness, legibility, and timeliness of the data reported.

All source documents should be completed in a neat, legible manner to ensure accurate interpretation of data.

Data will be collected using a password-protected, centralized electronic case report form called **ON-line Clinical Oncology Research Environment = Oncore.**] Data recorded in the electronic case report form (eCRF) derived from source documents should be consistent with the data recorded on the source documents.

11.2.2 Study Records Retention

Record retention will be in accordance with IRB-HSR and institutional policies.

11.3 Publication and Data Sharing Policy

This trial will be registered at clinicaltrials.gov, and results information from this trial will be submitted to clinicaltrials.gov. In addition, every attempt will be made to publish results in peer-reviewed journals. This study will be conducted in accordance with the National Institutes of Health (NIH) Public Access Policy, which ensures that the public has access to the published results of NIH funded research. It requires scientists to submit final peer-reviewed journal manuscripts that arise from NIH funds to the digital archive [PubMed Central](#) upon acceptance for publication.

11.4 Conflict of Interest Policy

The independence of this study from any actual or perceived influence, such as by the pharmaceutical industry, is critical. Therefore, any actual conflict of interest of persons who have

Pre-Operative Window of Adjuvant Endocrine Therapy to Inform Radiation Therapy Decisions in
Older Women with Early-Stage Breast Cancer

Version Date: 21 February 2023

a role in the design, conduct, analysis, publication, or any aspect of this trial will be disclosed and managed. Furthermore, persons who have a perceived conflict of interest will be required to have such conflicts managed in a way that is appropriate to their participation in the design and conduct of this trial. The study leadership in conjunction with the institution has established policies and procedures for all study group members to disclose all conflicts of interest and will establish a mechanism for the management of all reported dualities of interest.

Pre-Operative Window of Adjuvant Endocrine Therapy to Inform Radiation Therapy Decisions in Older Women with Early-Stage Breast Cancer

Version Date: 21 February 2023

13 APPENDICES

Pre-Operative Window of Adjuvant Endocrine Therapy to Inform Radiation Therapy Decisions in Older Women with Early-Stage Breast Cancer

Version Date: 21 February 2023

Appendix 1: Schedule of Events

Procedures	Screening	Pre_ET Period ^c			Pre-Op Visit	Surgery ⁱ	Radiation	Adjuvant Treatment Period			
Timeframe	≤ 21 days prior to registration unless otherwise noted	Day 1	Day 30 (+/- 7 d)	Day 90 (+/- 7 d)		2-8 weeks after Day 90 ^j		Visit 1 (1-90 days after surgery, chemotherapy completion, or RT completion ^b whichever is later)	Visit 2 (6 months after visit 1) (+/- 30 d)	Visit 3 (12 months after visit 1) (+/- 30 d)	Visit 4 (24 months after visit 1) (+/- 30 d)
Informed consent	X										
Demographics	X										
Medical history	X										
Physical exam /vitals	X		X	X	X			X	X	X	X
Endocrine Therapy		Taken daily as directed ⁱ						--Taken daily as directed ^d --			
BCS						X					
Radiation Therapy							X ^b				
Adverse event review and evaluation			X	X	X ^g						
Patient Beliefs Qs		X									
PRO Surveys	X ^a	X	X					X	X	X	X
Treatment Decision Survey								X			
Subject RT preference question		X			X						
Surgeon RT preference question		X ^h			X						
Radiation Oncologist RT preference question		X ^{f,h}			X ^f						
Decisional Conflict Scale		X			X						
Decision Regret Scale									X	X	X
Recurrence/Survival ^e								X	X	X	X

^a Patient reported outcome surveys should be completed prior to first dose of endocrine therapy.

^b Radiation therapy will be scheduled and administered in accordance with standard clinical practice and as recommended by the treating radiation-oncologist.

^c For patients who do not tolerate pre_ET and discontinue early, they will continue to be followed as indicated in the schedule above beginning at the pre-op visit.

Pre-Operative Window of Adjuvant Endocrine Therapy to Inform Radiation Therapy Decisions in Older Women with Early-Stage Breast Cancer

Version Date: 21 February 2023

^d Some individuals may choose to refuse adjuvant endocrine therapy, but will continue to be followed as indicated in the schedule above. Some Individuals will continue beyond 24 months of endocrine therapy as directed by their oncologist based on standard of care recommendations.

^e Tumor imaging will not be required at visits 1-4 to assess recurrence. Recurrence will be assessed using data from breast examinations conducted during the visit and prior results from imaging completed as part of standard clinical practice.

^f This is not applicable if participant has not been seen by Radiation Oncology prior to starting pre-ET (radiation oncology consultation on or before Day 1).

^g After the day 90 visit but prior to surgery.

^h Questionnaire to be completed on day 1 or within +7 days.

ⁱ After the day 90 visit, participants may continue the pre-operative endocrine therapy until 2 weeks before surgery per clinician discretion based on standard of care recommendations for the pre-operative treatment.

^j Participants need to be off endocrine therapy for at least 2 weeks and no more than 8 weeks prior to surgery

Pre-Operative Window of Adjuvant Endocrine Therapy to Inform Radiation Therapy Decisions in Older Women with Early-Stage Breast Cancer

Version Date: 21 February 2023

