3 OBJECTIVES AND ENDPOINTS

Objectives	Endpoints
Primary	

• To assess whether pre-ET changes an individual's preference for adjuvant radiation treatment• To assess whether pre-treatment with endocrine therapy changes the surgical oncologist's preference for adjuvant radiation treatment	
• Radiation preference question for participant pre and post pre-ET treatment• Radiation preference question for the surgical oncologist pre and post pre-ET treatment
Secondary	

• To obtain preliminary estimates to assess whether patient reported outcomes during pre-ET are predictive of long-term adjuvant endocrine therapy adherence• For those participants who agree to a radiation oncologist consultation, to assess whether pre-treatment with endocrine therapy changes the radiation oncologist's preference for adjuvant radiation treatment	
• PRO assessments• Radiation preference question for the radiation oncologist pre and post pre-ET treatment
Exploratory	

• To obtain preliminary data on the effect of pre-ET on decision outcomes for adjuvant therapy after BCS	
• PRO assessments
Exploratory	

• To obtain exploratory data on recurrence-free survival and overall survival	
• Recurrence-free survival and survival through 24 months

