6.2 Dosing and Administration

6.2.1 Endocrine Therapy

The dosing and administration of endocrine therapy will be in accordance with the drug label for each drug prescribed by the medical oncologist.

Individuals will not switch endocrine therapies during pre-operative endocrine therapy; however, an individual may stop endocrine therapy at any time during pre-operative therapy. Individuals who stop neo-adjuvant therapy prior to 90 days may still be eligible to receive adjuvant endocrine therapy.

Individuals may take different endocrine therapies during neo-adjuvant and adjuvant therapy.

Pre-Operative Window of Adjuvant Endocrine Therapy to Inform Radiation Therapy Decisions in Older Women with Early-Stage Breast Cancer

Version Date: 21 February 2023

Individuals may also switch endocrine therapies (e.g. switch from an aromatase inhibitor to tamoxifen) during adjuvant therapy.

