7.3 Procedures for Discontinuation of Study Intervention

Discontinuation from endocrine therapy or radiation therapy does not mean discontinuation from the study, and remaining study procedures should be completed as indicated by the study protocol. If a clinically significant finding is identified (including, but not limited to changes from baseline) after enrollment, the investigator or qualified designee will determine if any change in participant management is needed. Any new clinically relevant finding will be reported as an adverse event (AE).

The data to be collected and procedures to be completed at the time of study intervention discontinuation are included in the schedule of events ([Appendix 1](#)).

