10.2 Endpoints, Statistical Hypotheses and Estimation

Assessment of the primary study objectives will be based upon answers to the radiation preference question for study participants and surgical oncologists separately. Change in preference is measured as a binary variable (yes/no) with a coding of 'yes' if answers between the pre-op and on-study (baseline) response differ (no to yes; or yes to no). No difference in response is coded as 'no'.

Hypothesis test 1: To determine if pre-treatment with endocrine therapy changes participant preference for adjuvant radiation treatment in the participant study population by at least 10% with a one-sided binomial test.

Hypothesis test 2: To determine if pre-treatment with endocrine therapy changes surgical oncologist preference for participant specific adjuvant radiation treatment in the participant study population by at least 10% with a one-sided binomial test.

Estimation: To estimate the association of pre-treatment PRO measures on the probability of long-term adjuvant endocrine therapy adherence.

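### Women who stop pre-ET early skip its remaining PRO surveys, with none set at stopping or pre-op; footnote c and Section 7.3 need reconciling

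*Combined protocol and SAP*

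**What the plan says.** Section 6.2.1 allows early stopping: "an individual may stop endocrine therapy at any time during pre-operative therapy". For women who do not tolerate pre-ET and stop early, footnote c of Appendix 1 says "they will continue to be followed as indicated in the schedule above beginning at the pre-op visit".

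The PRO row of Appendix 1 has three marks before surgery and then adjuvant Visits 1 to 4. As printed, the three marks stand at Screening, Day 1 and Day 30. They may have slipped one column from Day 1, Day 30 and Day 90. The first carries the note "Patient reported outcome surveys should be completed prior to first dose of endocrine therapy". Under either reading there is no mark at Pre-Op, Surgery or Radiation.

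Section 7.3 says two things about a woman who stops. First, stopping therapy is not leaving the study, and "remaining study procedures should be completed as indicated by the study protocol". Second, "The data to be collected and procedures to be completed at the time of study intervention discontinuation are included in the schedule of events". That table has no discontinuation visit or column.

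The first secondary objective in Section 3 is "To obtain preliminary estimates to assess whether patient reported outcomes during pre-ET are predictive of long-term adjuvant endocrine therapy adherence". The estimation statement in Section 10.2 is worded differently: "To estimate the association of pre-treatment PRO measures on the probability of long-term adjuvant endocrine therapy adherence". Section 10.5.2 adds exploratory repeated-measures models of change over time. No method is given for missing PROs.

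**The concern.** The objective depends on PROs taken while the woman is on pre-ET. Read literally, footnote c skips whatever pre-ET surveys remain for women who stopped because they did not tolerate the drug, and puts nothing in their place. These women plausibly lie toward the poor end of the tolerance scale, where a predictor of later non-adherence carries much of its information.

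The loss cannot be made good later. The next scheduled PRO is adjuvant Visit 1, 1 to 90 days after surgery, chemotherapy or radiation, whichever is latest. The questionnaires look back about one week (CESD-R and most EORTC items) or four weeks (BCPT-SCL and a few EORTC items), so they would generally miss the pre-ET period and pick up the effects of surgery or radiation instead.

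**Working it through.** **1. What each woman provides if footnote c is followed**

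| Time of stopping | Marks at Screening, Day 1, Day 30 | Marks at Day 1, Day 30, Day 90 |
|---|---|---|
| Before Day 30 | Baseline only | Baseline only |
| Day 30 to before Day 90 | Baseline and Day 30; nothing scheduled is lost | Baseline and Day 30; Day 90 is lost |

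The absence of any on-treatment PRO for women who stop before Day 30 holds under both readings. A lost Day 90 PRO depends on the second, so no conclusion is rested on it.

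**2. The plan's own power figure (Section 10.3)**

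Inputs: n = 70, event probability 0.25, odds ratio 2, 5% level, stated power 80%. The plan gives neither the unit of the odds ratio nor the sidedness; one SD of the score is assumed. Formula: power = Φ(√(n·p·(1−p))·ln OR − z).

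- √(70 × 0.25 × 0.75) × ln 2 = 3.623 × 0.693 = 2.511
- One-sided: Φ(2.511 − 1.645) = 80.7%, which reproduces the plan.
- Two-sided: Φ(2.511 − 1.960) = 70.9%.

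**3. Effect of losing on-treatment PROs**

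The documents give no early-stop rate, so a range is shown. Logistic simulation: n = 70, standard normal score, non-adherence as the event at about 25% (intercept −1.22), odds ratio 2 per SD, 2,000 repetitions (simulation error about one point). Women without an on-treatment PRO are dropped from the model. They are chosen by a variable with correlation 0, 0.8 or 1 with the score. With no loss, power is 63% two-sided and 76% one-sided, below the formula values, which are large-sample approximations.

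| Lost | Women | Two-sided power at correlation 0 / 0.8 / 1 | One-sided power at correlation 0 / 0.8 / 1 |
|---|---|---|---|
| 5% | 4 | 59 / 51 / 45% | 73 / 65 / 59% |
| 10% | 7 | 57 / 45 / 37% | 71 / 59 / 52% |
| 20% | 14 | 50 / 35 / 24% | 64 / 49 / 38% |

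Repeat runs at 10% lost gave 58% two-sided for random loss and 38% for loss of exactly the worst scorers. The median estimated odds ratio stayed between 2.0 and 2.1 in every setting.

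**4. Which outcome is 25%**

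Section 10.3 applies 25% to adherence, whereas the simulation applies it to non-adherence. The formula is the same either way, because p(1−p) is symmetric, but selective loss is not. With non-adherence at 75% (intercept +1.21, 6,000 repetitions), two-sided power is again about 63% with complete data. At 10% lost it is 57% for random loss, 53% at correlation 0.8 and 51% at correlation 1. The lower bound of 37–38% therefore belongs to the reading with 25% non-adherent.

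**5. Does the pausing guideline keep the gap small?**

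Section 10.5.3 pauses the study at half accrual (41 or 42 of 83) if the upper 90% limit for pre-ET adherence is below 80%. With Clopper-Pearson limits, 27 of 41 adherent gives an upper limit of 78.0% and 28 of 42 gives 78.6%. The guideline first acts at 14 non-adherent women (33–34%), so it does not bound early stopping tightly.

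**The case against.** A reader might infer that tolerance data are missing for exactly the women who tolerated pre-ET worst. The documents do not support that.

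- Women who stop after Day 30 have the Day 30 PRO and, as the table is printed, lose nothing scheduled. The only timing figure in the documents, from the adjuvant aromatase inhibitor trial described in Section 2.2.4, is a median of 6.4 months to discontinuation. That suggests stopping before Day 30 is uncommon, though it is not evidence about pre-ET itself.
- Stop dates and reasons are recorded (Section 8.1.1), and adverse events are reviewed at the pre-op visit.
- Section 7.3 can be read as keeping the remaining surveys in place. On that reading the plan contradicts itself; it does not clearly remove the data.
- The adherence analysis set in Section 10.5.1(c) needs only on-study PROs and adherence data, and Section 10.2 speaks of pre-treatment PROs. Early stoppers stay in the set, and baseline models are untouched.
- Section 10.5.3 expects pre-ET adherence close to 100%, and this is a pilot seeking preliminary estimates.

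All of this stands and limits the point. It does not remove it. Stop reasons and adverse events are not the PRO predictor. Section 2.2.5 reports musculoskeletal burden only rising at month 1 and significantly higher by month 3, so Day 30 alone is an incomplete substitute. And the reading of Section 7.3 that would keep the surveys is the one footnote c contradicts.

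**Conclusion.** The gap is real and limited. Under footnote c, women who stop before Day 30 have no on-treatment PRO, and later stoppers may lack the last one. Section 7.3 points to discontinuation procedures that do not exist and pulls the other way on remaining procedures. What suffers is the secondary objective on PROs during pre-ET and the change-over-time models. The primary endpoint is unaffected, because early stoppers still answer the radiation preference question at the pre-op visit.

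The size depends on an unknown early-stop rate. At an assumed 10%, two-sided power falls from about 63% to somewhere between 57–58% and 37–38%. The lower end is a bound: it assumes that the women lost are exactly the worst scorers, that none has an on-treatment PRO, and that 25% are non-adherent. If stopping is as rare as Section 10.5.3 expects, the loss is small.

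Two further inferences should be resisted. The lower figures are not a forecast. Nor do the simulations show a biased odds ratio: when loss depends on the score, the estimate stays near 2, and the harm is lost precision.

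**What to change.** This is a cheap improvement.

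- **Appendix 1 and Section 7.3:** reconcile the two passages. Require the existing PRO set (EORTC, BCPT-SCL, CESD-R and the adherence items) when a woman reports stopping pre-ET before Day 90, in person or remotely, with the date recorded. If that moment is missed, give it at the next contact or the pre-op visit, flagged with days since last dose.
- **Section 10.5.2:** for early stoppers, use the last PRO taken on pre-ET, or at stopping within the questionnaires' recall window, as the tolerance value. A later pre-op PRO may record recovery and should not be entered as tolerance. Add a sensitivity analysis with early stopping itself as a predictor.

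The cost is a short amendment and one extra questionnaire set for the few women who stop early, at a contact that may not be a scheduled visit. Treatment is unchanged.
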